5. TREATMENTS

5.1. Treatments Administered

Study drug will be administered by the Subject or the Subject's caregiver only in accordance with the procedures described in this protocol and in the Instructions for Use.

5.2. Identity of Investigational Product(s)

Study Drug: Furoscix, (Furosemide Injection), 80 mg/10 mL is a proprietary furosemide formulation that is buffered to a neutral pH to enable subcutaneous administration and contained in a prefilled, Crystal Zenith (CZ) cartridge.

Furoscix (Furosemide Injection), 10 mL buffered furosemide solution (8 mg/mL), is manufactured by Swissfillon AG, [name] under good manufacturing practice conditions. Contains Tris Hydrochloride and may contain Sodium Chloride Hydrochloric Acid for pH adjustment: pH 7.4 (range 7.0 to 7.8).

Study device: The Infusor is a compact, ethylene oxide (EtO) sterilized, single-use, electro-mechanical (battery powered, micro-processor controlled), on-body subcutaneous delivery system based on the SmartDose Gen II 10 mL (West Pharmaceutical Services).

The Furoscix Infusor is an investigational drug-device combination product. The Infusor is applied to the abdomen via a medical grade adhesive and delivers a subcutaneous infusion of Furoscix through a pre-programmed, biphasic delivery profile with 30 mg (3.75 mL) administered over the first hour, followed by 12.5 mg (1.56 mL) per hour for the subsequent 4 hours (Total dose is 80 mg (10 mL) over 5 hours).

5.2.1. Labeling

Study drug (Furosemide Injection (Furoscix)) and study device (On-Body Infusor) will bear labels that meet applicable laws for an investigational drug-device combination, which may include, but is not limited to, the following information:

- Federal law statement
- Batch number
- Storage information

Study specific instructions for the use and operation of the product will be available to the PI, study staff and subjects. These materials will be based on the Furoscix Infusor Instructions for Use of the study product as it exists at the time of the study.

5.2.2. Storage and Handling

Store study drug at 15° - 30°C, (59° - 86°F). Protect from Light.

5.3. Method of Assigning Subjects to Treatment Groups

5.3.1. Treatment Assignment/Randomization

Subjects will be randomly assigned (2:1) to receive the Furoscix Infusor or continued medical therapy.

5.4. Selection of Doses in the Study

The dose of 80 mg is the fixed dose of Furoscix. This was selected based on clinical criteria and physician prescribing and is consistent with the approved labeling of furosemide injection, United States Pharmacopeia. The dosing frequency and duration of the initial therapy will be determined by the investigator based on an estimated volume of diuresis desired to transition Subject back to their oral maintenance diuretic therapy. The total duration in days and number of doses will be determined by the treating investigator based on an estimated volume of diuresis desired to transition Subject back to their oral maintenance diuretic therapy.

After Subjects have been transitioned to their oral maintenance diuretic regimen, additional doses of Furoscix can be prescribed during the 30-day study period as needed based on the presence of symptoms of congestion (dyspnea, edema, and/or excess weight gain) as determined by the investigator. No more than 7 doses of Furoscix is permitted during the 30-day study period. Additional doses beyond 7 requires approval by the medical monitor.

5.5. Selection and Timing of Dose for Each Subject

Furoscix will be administered daily via the Furoscix Infusor whereby 80 mg is administered subcutaneously over 5 hours in a biphasic regimen (30 mg in the first hour, followed 12.5 mg/hour for the subsequent 4 hours). Within a single 24-hour period, the 80 mg dose can be repeated at the discretion of the investigator ≥ 2 hours after the completion of the first dose. The dosing frequency and duration of the initial therapy will be determined by the investigator based on an estimated volume of diuresis desired to transition Subject back to their oral maintenance diuretic therapy.

After Subjects have been transitioned to their oral maintenance diuretic regimen, additional doses of Furoscix can be prescribed during the 30-day study period as needed based on the presence of symptoms of congestion (dyspnea, edema, and/or excess weight gain) as determined by the investigator. No more than 7 doses of Furoscix is permitted during the 30-day study period. Additional doses beyond 7 requires approval by the medical monitor. If diuretic modifications are made after Subjects' are transitioned to their oral maintenance diuretic regimen, including additional doses of Furoscix in the treatment group or oral diuretics for the treatment as usual control group, the Subjects' follow-up assessments and timing of those assessments will be based on the investigator's clinical judgement.

Subjects will be instructed on the use of the Furoscix Infusor by the investigator and/or study staff in accordance with the IFU and subject specific instructions. The initial dose of the study product may be administered in the clinic or at home on the day of enrollment. Additional doses will be provided to the subject for self-administration or administration by a caregiver in the home setting as directed by the investigator or study staff.

5.6. Procedures for Blinding

This is an open label study.

5.7. Prior and Concomitant Therapy

Prior and concomitant therapy will include all prescription medications and therapies. All information on prior (within the past 48 hours) and concomitant therapies will be recorded in the Subject's source and on the Subject's CRF. They should include the name of the therapy or drug and duration of the treatment (start and stop dates).

5.8. Prohibited Medications

Concomitant use of any drugs known to interact with furosemide, including aminoglycoside antibiotics, ethacrynic acid, high doses of salicylates, cisplatin, tubocurarine, succinylcholine, chloral hydrate, phenytoin, methotrexate, indomethacin and lithium is not permitted.

5.9. Other Restrictions

Subjects are advised to avoid strenuous physical activity or activities that could expose the device to moisture such as swimming, bathing or showering. Subjects will be informed that marked diuresis may ensue after activation, and that they should avoid travel, operating a vehicle or other situations without immediate access to bathroom facilities.

5.10. Study Stopping Criteria

The study may be stopped if the Investigator, Medical Monitor, Sponsor or IRB determines that subject safety may be compromised by continuing in the study.

5.11. Treatment Compliance

Preparation, fill and placement of the Euroscix Infusor will be done in accordance with the study specific instructions which are based on the Instructions for Use of the study product as it exists at the time of the study. Site staff will perform product accountability (count the number of units used versus the number of days the subject was instructed to administer the study product). Study staff will also inspect the units and cartridge(s) used by the subjects to report/confirm they are empty.

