2. STUDY OBJECTIVES

The objectives of this study are:

Primary Objective:

- To provide pilot data on the effectiveness and safety to inform a pivotal trial

Secondary Objectives:

- To inform population enrichment strategies
- To refine pivotal trial endpoints and analytical methods
- To identify operational challenges of study design
- To assess patient adherence, competence, and experience
- To familiarize staff and patients with device application and use

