3.2. Furoscix Infusor

The Furoscix Infusor is a drug-device combination product consisting of Furoscix (Furosemide injection, 80 mg per 10 mL), a novel, pH neutral furosemide formulation optimized for subcutaneous administration and contained in a prefilled, Crystal Zenith (CZ) cartridge, and a proprietary wearable, pre-programmed on-body delivery system, the Infusor, based on the SmartDose Gen II 10 mL (West Pharmaceutical Services).

The Infusor is a compact, ethylene oxide (EtO) sterilized, single-use, electro-mechanical (battery powered, micro-processor controlled), on-body delivery system that administers a fixed dose of drug product from a prefilled cartridge assembly into subcutaneous tissue of the abdomen. It is intended for use by patients, caregivers, or a health care professional (HCP) at home or in a clinic setting.

The Furoscix Infusor is 117 mm x 62 mm x 30 mm (length x width x height) and weighs approximately 80 grams without the drug cartridge and 90 grams, with a filled drug cartridge inserted into the drug compartment. It has an integrated, adhesive patch which attaches the Infusor to the skin for dose administration. The device with adhesive is removed from the skin following completion of the dose and discarded.

The system delivery parameters will be pre-programmed as part of the manufacturing process to deliver 80 mg (10 mL) furosemide over 5 hours using a biphasic delivery profile of 30 mg furosemide (3.75 mL) over the first hour and 12.5 mg furosemide (1.56 mL) per hour over the subsequent 4 hours. The device elements are shown in [Figure 1](#).

[figure not shown]

Figure 1: Main components of Furoscix On-Body Infusor

The Furoscix Infusor utilizes a primary container, which consists of the CZ cartridge (CZ barrel and elastomeric septum) and elastomeric piston. The primary container assembly is prefilled with the Furoscix as part of the fill-finish process.

Following removal of the Furoscix Infusor from the packaging, the drug compartment of the device is opened by the user, which turns the device on, and a built-in self-test is performed to verify the needle/button position, correct software parameters, the device was not operated prior to the current activation and the motor and batteries are functional.

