### **15.3.9 Device and Product Accountability**

Device and product accountability will be summarized using descriptive statistics such as n, mean, median, minimum, and maximum for continuous variables and count and percentages will be provided for categorical variables by treatment group and overall for the Safety Population. A listing will be provided for device and product accountability, including details about the kit dispensing for the Safety Population.

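### Protocol 5.11 checks units used against days instructed, which overstates adherence for subjects instructed to take a second dose within 24 hours (minor)

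*Protocol*

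**What the plan says.** Protocol 5.11 gives one quantitative check on compliance. Site staff perform product accountability, described as: "count the number of units used versus the number of days the subject was instructed to administer the study product". They also inspect used units and cartridges to confirm that these are empty.

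The dosing sections set the background. The default in Protocol 5.5 is one dose a day: "Furoscix will be administered daily via the Furoscix Infusor whereby 80 mg is administered subcutaneously over 5 hours". The same section then allows a repeat: "Within a single 24-hour period, the 80 mg dose can be repeated at the discretion of the investigator". Protocol 3.1 and 6.2 and SAP section 2 carry the same repeat rule. Protocol 3.2 describes the infusor as a single-use "on-body delivery system that administers a fixed dose of drug product from a prefilled cartridge assembly", so one unit is one dose. Protocol 5.4 treats days and doses as two quantities: "The total duration in days and number of doses will be determined by the treating investigator". It also sets a limit, which the medical monitor may extend: "No more than 7 doses of Furoscix is permitted during the 30-day study period".

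Adherence is among the secondary objectives in Protocol section 2: "To assess patient adherence, competence, and experience". SAP 6.2 repeats it. The SAP defines no adherence or compliance measure. Its nearest text is section 15.3.9: "Device and product accountability will be summarized using descriptive statistics", together with a listing that includes kit dispensing.

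**The concern.** Comparing units with days is sound only if each instructed day calls for one unit. A day with an instructed repeat calls for two. For such a subject the comparator in 5.11 is too small: full adherence looks like over-use, and a missed dose can be offset by the uncounted repeat.

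At stake is the adherence part of a secondary objective, in a pilot meant to inform a pivotal trial. No SAP definition replaces the 5.11 comparison, and the rule could be carried into the later protocol. The point concerns the measure only and takes no position on how often the product should be given.

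**Working it through.** The documents state no adherence figure, so there is none to reproduce. The check is direct arithmetic.

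**Inputs**
- One unit = one 80 mg dose (Protocol 3.2).
- Repeat dosing within 24 hours is allowed (Protocol 5.5, SAP section 2).
- At most 7 doses in 30 days without medical monitor approval (Protocol 5.4).
- 34 subjects planned for Furoscix (SAP section 4).
- Assumption: no more than one repeat on any day, so R ≤ D.

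**Formulas.** Let D = days instructed, R = days with an instructed repeat, U = units used.
- Comparison by days, as in 5.11: U/D.
- Comparison by doses instructed: U/(D+R).
- Ratio of the first to the second: (D+R)/D = 1 + R/D. This is 1 when R = 0, so the count is correct for subjects with no instructed repeat.

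**Examples within the 7-dose limit**

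| D | R | Doses instructed | All taken, by days | All taken, by doses | One missed, by days | One missed, by doses |
|---|---|---|---|---|---|---|
| 6 | 1 | 7 | 7/6 = 116.7% | 100% | 6/6 = 100% | 6/7 = 85.7% |
| 3 | 1 | 4 | 4/3 = 133.3% | 100% | 3/3 = 100% | 3/4 = 75% |
| 2 | 1 | 3 | 3/2 = 150% | 100% | 2/2 = 100% | 2/3 = 66.7% |
| 1 | 1 | 2 | 2/1 = 200% | 100% | 1/1 = 100% | 1/2 = 50% |
| 3 | 3 | 6 | 6/3 = 200% | 100% | 5/3 = 166.7% | 5/6 = 83.3% |

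The inflation factor therefore runs from 7/6 = 1.17 to 2.00.

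**All combinations.** Twelve schedules have R ≥ 1, R ≤ D and D+R ≤ 7. Letting U run from 1 to D+R gives 62 combinations.
- U/D exceeds U/(D+R) in 62 of 62.
- Dropping the 12 fully adherent combinations leaves 62 − 12 = 50 with missed doses.
- In 20 of these 50, U/D is still 100% or more. These are the values of U from D to D+R−1, R of them per schedule.
- Each of the 12 schedules has one under-dosed value, U = D, that reads exactly 100%. The other 20 − 12 = 8 read above 100%.

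These are counts of possible patterns, not probabilities. The documents give no expected frequency of repeat dosing.

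**The case against.** The strongest reply is that 5.11 describes a site reconciliation, not a statistic. It sets no ratio, percentage or threshold, and every percentage above comes from dividing the two counts. That stands, and is why the point is limited to figures built from this comparison.

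Second, a reader might infer that SAP 15.3.9 will tabulate units per day because both sections speak of product accountability. The documents do not show this. Section 15.3.9 neither cites 5.11 nor mentions days, and Protocol 5.12 and 9.1.11 use accountability for receipt, dispensing and return of product.

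Third, a reader might infer that the trial cannot report adherence correctly. That goes too far. The diary (Protocol 6.2.24) records the kit serial number and the start and stop of each dose, used units are returned and inspected, and SAP 15.2.1.1 already uses number of doses as a variable. A dose-based figure can be built if the number of doses instructed is also recorded. These sources describe doses taken or supplied, however, and neither document lists doses instructed as an item to record. Section 5.11 points sites to days.

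Fourth, readings of 133% or 200% would stand out and prompt a query. That holds for readings above 100%. It does not hold for the 12 under-dosed patterns that read exactly 100%.

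Finally, a reader might take the count to be wrong for every subject who used two units in a day. It is not: a second unit taken without instruction is correctly shown as excess. Only instructed repeats are misread.

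**Conclusion.** The comparator in Protocol 5.11 does not fit the repeat-dose rule. For a subject instructed to repeat a dose who used at least one unit, an adherence figure based on it is inflated by 1.17 to 2.00 within the 7-dose limit, assuming at most one repeat per day. It can show full compliance when doses were missed.

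Severity is minor. The count enters no primary or secondary endpoint, and the Per-Protocol population in SAP section 14 asks for only one dose, with no compliance threshold. The default is daily dosing, for which the count is right. The number affected cannot be computed and lies between 0 and 34. The documents support a mismatched comparator for one secondary objective. They do not support a claim that a planned adherence result is already wrong or that adherence data are lost.

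**What to change.** In Protocol 5.11, change the comparator from days to the number of doses the subject was instructed to take. Record the doses instructed for each subject. In SAP 15.3.9, define the per-subject ratio of units used to doses instructed and summarise it for the Furoscix group. Report partly delivered or interrupted units separately: Protocol 3.2 foresees interrupted infusions and detached devices, and a plain unit count would treat these as full doses.

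The cost is one extra recorded item and short wording changes in both documents. The protocol change needs a sponsor amendment and IRB approval (Protocol 9.2.2), so it is best combined with other changes. Asking sites to record doses instructed as they are prescribed is easier than recovering the number later from source notes.

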5.12. Study Drug-Device Combination Accountability

The study drug-device combination product will be handled in accordance with the procedures of this protocol. Only subjects enrolled in the study may receive study drug-device combination product, in accordance with applicable regulatory requirements.

Study staff authorized to handle and store the drug-device combination product must keep an accurate accounting of the receipt, disposition and return of the study products received from the sponsor and dispensed to subjects. Drug-device combination product accountability will be assessed by the study monitor during periodic monitoring visits.

6. STUDY PROCEDURES

6.1. Study Measurements and Assessments

6.1.1. Assessment of Primary Endpoints

- Improvement in a composite/combined morbidity/mortality endpoint at 30 days using the Finkelstein-Schoenfeld method.
 - CV death
 - HF hospitalization
 - Urgent ED/Clinic visit for worsening heart failure (defined as IV diuretics, augmentation of or new administration of metolazone)
 - Change in NT-proBNP from baseline at Day 7
- Incidence of Adverse Events, Adverse Events of Special Interest, and Serious Adverse Events

6.1.2. Assessment of Secondary Endpoints (through 30 days)

- Days alive and HF event free days
- Global Visual Analog Scale
- Composite Congestion Score
- 5-point Current Dyspnea Score
- 7-point Dyspnea Score
- Health-related quality of life (KCCQ-12)
- Renal Function and Electrolytes
- Weight

- Exercise tolerance (6MWT)
- % Lung Fluid Measurement via Remote Dielectric Sensing (ReDS)

6.1.3. Assessment of Adverse Events of Special Interest

Subjects will have blood drawn at each clinic visit to monitor safety parameters. Subjects will specifically be monitored for the following adverse events:

- Worsening kidney function, defined as increase of ≥ 0.5 mg/dl in serum creatinine
- Hyperkalemia, defined as $K > 5.5$ mEq/L
- Hypokalemia, defined as $K < 3.5$ mEq/L
- Hypomagnesemia, defined as $Mg < 1.5$ mg/dL

6.2. Study Phases and Procedures

A Time and Events Schedule is provided in [Appendix 1](#).

The Screening Phase will be conducted in the clinic. All Subjects who sign the informed consent form and satisfy the inclusion/exclusion criteria will be enrolled into the trial on the same day as screening. NT-proBNP will be sent to centralized laboratory. Drug administration will start on the day of screening and enrollment after randomization.

The Treatment Phase will begin upon completion of screening through Day 29. Furoscix will be administered via the Furoscix Infusor whereby 80 mg is administered subcutaneously over 5 hours in a biphasic regimen (30 mg in the first hour, followed 12.5 mg/hour for the subsequent 4 hours). Within a single 24-hour period, the 80 mg dose can be repeated at the discretion of the investigator ≥ 2 hours after the completion of the first dose. Subjects should be transitioned back to their oral maintenance diuretic regimen when clinically indicated at the discretion of the investigator. After Subjects have been transitioned to their oral maintenance diuretic regimen, additional doses of Furoscix can be prescribed during the 30-day study period as needed based on the presence of congestion symptoms (dyspnea, edema, and/or excess weight gain) as determined by the investigator. No more than 7 doses of Furoscix is permitted during the 30-day study period. Additional doses beyond 7 requires approval by the medical monitor.

Prior to leaving the clinic on Day 0, the Subject and/or caregiver will be trained by the study staff on how to prepare the study product and apply it to their abdomen and remove it once the infusion is completed. The initial dose of the study product may be administered in the clinic or at home on the day of enrollment. Additional doses will be provided to the Subject for self-administration or administration by a caregiver in the home setting as directed by the investigator or study staff.

Subjects will be seen in the clinic on Day 0, 1, 3* and 7 and will receive phone calls on Days 2, 4, 5, 6 and 17 where the study staff will assess subject's signs and/or symptoms of congestion. These visits should all be conducted as early in the day as possible to accommodate the 5-hour infusion. If Day 3 falls on a Saturday or Sunday, subjects may be seen in the clinic and have Day 3 assessments completed on either Day 2 (Friday, if Day 3 falls on Saturday) or Day 4 (Monday, if Day 3 falls on Sunday). On Day 3 the subject will have a phone call visit.

After the Day 7 clinic visit, subjects will be instructed to continue utilize provided equipment to weigh themselves and record their blood pressure and heart rate approximately same time each morning. If their symptoms worsen after they are transitioned to their oral maintenance diuretic regimen, they will be instructed to contact the investigator. Site staff will determine

based on the presence of congestion symptoms (e.g. dyspnea, edema, and/or excess weight gain) if Subjects' diuretic regimen should be modified, including additional doses of Furoscix in the treatment group or oral diuretics for the treatment as usual control group. The Subjects' follow-up assessments and timing of those assessments will be based on the investigator's clinical judgement. Unscheduled clinic and phone visits can be conducted as needed.

The Follow-up Phase will consist of a one-day visit on Day 30 \pm 5 days post randomization (in-clinic visit).

6.2.1. Screening (Day 0)

The initial Screening assessment will be conducted the same day as the start of the Treatment Phase.

The following procedures/assessments will be performed at Screening:

- Informed consent (must be done prior to **any** of the following procedures)
- Eligibility review
- Medical history and Subject demographics (date of birth, gender, ethnic origin and race)
- Limited Physical Exam including NYHA Classification
- Composite Congestion Score (CCS)
- 5-point Current Dyspnea Score (using the script - [Appendix 7](#))
- Weight and height (Calculate BMI)
- Vital Signs
- % Lung Fluid Measurement (ReDS)
- Venous blood for clinical chemistries, hematology (run locally for eligibility), NT-proBNP (run locally for eligibility; 2nd sample sent to a centralized laboratory for subjects who qualify to participate)
- Urine pregnancy test on females of childbearing potential
- Administer the Kansas City Cardiomyopathy Questionnaire (KCCQ-12)
- Administer the patient global assessment visual analog scale (VAS)
- Administer Six Minute Walk Test (6MWT)
- Assess for adverse events
- Record concomitant medications (all medications taken within 48 hours)
- Schedule next study visit (Day 1).

